1.1 Does the protocol specify timelines for				
1.1.1 Start of data collection ¹				17
1.1.2 End of data collection ²				17

Section 1: Milestones	Yes	No	N/A	Page Number(s)
1.1.3 Study progress report(s)				1717
1.1.4 Interim progress report(s)				
1.1.5 Registration in the EU PAS register				
1.1.6 Final report of study results.				

Comments:

Registration is planned prior to study initiation once the protocol is final and approved by BfArM

Section 2: Research question	Yes	No	N/A	Page Number(s)
2.1 Does the formulation of the research question and objectives clearly explain:				
2.1.1 Why the study is conducted? (e.g. to address an important public health concern, a risk identified in the risk management plan, an emerging safety issue)				13, 18
2.1.2 The objective(s) of the study?				13, 20
2.1.3 The target population? (i.e. population or subgroup to whom the study results are intended to be generalised)				13, 22
2.1.4 Which formal hypothesis(-es) is (are) to be tested?				
2.1.5 If applicable, that there is no a priori hypothesis?				

Comments:

Section 3: Study design	Yes	No	N/A	Page Number(s)
3.1 Is the study design described? (e.g. cohort, case-control, randomised controlled trial, new or alternative design)				13, 20
3.2 Does the protocol specify the primary and secondary (if applicable) endpoint(s) to be investigated?				
3.3 Does the protocol describe the measure(s) of effect? (e.g. relative risk, odds ratio, deaths per 1000)				

Section 3: Study design	Yes	No	N/A	Page Number(s)
person-years, absolute risk, excess risk, incidence rate ratio, hazard ratio, number needed to harm (NNH) per year)				

Comments:

Only descriptive statistics will be done, no statistical tests

Section 4: Source and study populations	Yes	No	N/A	Page Number(s)
4.1 Is the source population described?				13, 22
4.2 Is the planned study population defined in terms of:				22
4.2.1 Study time period?				23
4.2.2 Age and sex?				22
4.2.3 Country of origin?				22
4.2.4 Disease/indication?				
4.2.5 Co-morbidity?				
4.2.6 Seasonality?				
4.3 Does the protocol define how the study population will be sampled from the source population? (e.g. event or inclusion/exclusion criteria)				22

Comments:

All patients with a record of Flupirtine prescription during the defined time period will be included

Section 5: Exposure definition and measurement	Yes	No	N/A	Page Number(s)
5.1 Does the protocol describe how exposure is defined and measured?(e.g. operational details for defining and categorising exposure)				23
5.2 Does the protocol discuss the validity of exposure measurement? (e.g. precision, accuracy, prospective ascertainment, exposure information recorded before the outcome occurred, use of validation sub-study)				23
5.3 Is exposure classified according to time windows?(e.g. current user, former user, non-use)				
5.4 Is exposure classified based on biological mechanism of action and taking into account the pharmacokinetics and pharmacodynamics of the drug?				

Section 5: Exposure definition and measurement	Yes	No	N/A	Page Number(s)
5.5 Does the protocol specify whether a dose-dependent or duration-dependent response is measured?				

Comments:

--

Section 6: Endpoint definition and measurement	Yes	No	N/A	Page Number(s)
6.1 Does the protocol describe how the endpoints are defined and measured?				
6.2 Does the protocol discuss the validity of endpoint measurement? (e.g. precision, accuracy, sensitivity, specificity, positive predictive value, prospective or retrospective ascertainment, use of validation sub-study)				

Comments:

--

Section 7: Confounders and effect modifiers	Yes	No	N/A	Page Number(s)
7.1 Does the protocol address known confounders?(e.g. collection of data on known confounders, methods of controlling for known confounders)				
7.2 Does the protocol address known effect modifiers?(e.g. collection of data on known effect modifiers, anticipated direction of effect)				

Comments:

--

Section 8: Data sources	Yes	No	N/A	Page Number(s)
8.1 Does the protocol describe the data source(s) used in the study for the ascertainment of:				15
8.1.1 Exposure?(e.g. pharmacy dispensing, general practice prescribing, claims data, self-report, face-to-face interview, etc.)				
8.1.2 Endpoints?(e.g. clinical records, laboratory markers or values, claims data, self-report, patient interview including scales and questionnaires, vital statistics, etc.)				

Section 8: Data sources	Yes	No	N/A	Page Number(s)

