9.1. Study design

This drug utilisation study for Flupirtine will employ an analysis using a longitudinal database in Germany:

- Patient level electronic medical record (EMR) data (IMS[®] Disease Analyzer)

The IMS[®] Disease Analyzer provides both drug use data and information about patients' clinical characteristics, including indication, co-morbidities and laboratory tests in separate physician panels.

The study will be carried out in Germany as more than 90% of total prescriptions of flupirtine-containing medicinal products of MAHs in European Union Member States were issued in Germany.

The study will be set up as a pre-post design to compare flupirtine prescribing patterns (before and after the revision of SmPC).

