9.7 Data analysis

9.7.1 General remarks

Data from specialist panels will not be combined. The data will be analysed separately by panel (PCP and orthopaedist panel) and for the period before and after SmPC review.

All analyses will be stratified by incident and prevalent users.

Study tables will reference the data source used for each set of results. The data will be presented graphically where useful.

The statistical unit will be the patient (for information such as demographical and clinical characteristics, medical history, contraindications) and the Flupirtine prescription (for information such as indication, number of prescriptions, recommended treatment duration, concomitant drug prescriptions).

The statistical analysis will be done descriptively. Missing values will be reported as missing and no imputation will be conducted. Descriptive tables will be compiled for all variables. Continuous variables will be presented with counts, means, medians, standard deviations, and minimum and maximum values. Categorical variables will be presented in frequency tables. Rates and 95% confidence intervals will be provided when relevant.

Data will be analysed using the statistical software SAS (SAS Institute Inc., Cary, USA) with version 9.3 or above.

All results will be presented in tables. In addition, parameters addressing the primary objectives and eligible for a comparison of time periods (assessment period and reference period) with respect to the effect of risk minimisation measures (for example flupirtine treatment duration) will be presented graphically e.g. by displaying plots or bar charts.

The following section will describe the analyses and definitions used for the DA (**IMS[®] Disease Analyzer**) database.

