9.7.2.1 Patient characteristics of Flupirtine treated patients

The patient characteristics (age, gender, insurance private or SHI) of Flupirtine patients will be described.

- Number of patients within following age groups:
 - < 18 years
 - 18 to 29 years
 - 30 to 39 years
 - 40 to 49 years
 - 50 to 59 years
 - 60 to 69 years
 - 70 years and older

Analyses:

- Number and percentage of Flupirtine patients per age group, gender, insurance status(private or SHI insured)

Indication for flupirtine prescription

In order to describe the indication for flupirtine drugs all diagnoses related to the flupirtine prescriptions will be analysed.

- All diagnoses documented on the prescription of flupirtine will be defined as principal diagnosis.

As not for all prescriptions principal diagnoses will be available, additionally the following approaches will be chosen:

- If there is any disease associated with acute pain (Annex 3-ii) recorded in a time frame of 2 weeks around the date of prescription, this will be defined as associated diagnosis.
- If there is any disease associated with acute pain (Annex 3-ii) recorded in a 12 months history before the date of prescription, this will be defined as co-morbidity.

Principal diagnoses, associated diagnoses and co-morbidities will be analysed separately.

The findings of principal diagnoses will be grouped by diagnosis according to ICD-10 codes (selection of codes see Annex 3) including diseases associated with acute pain and chronic pain.

Analysis:

- Number and percentage of prescriptions, stratified by diagnosis (only principal diagnoses)
- Number and percentage of prescriptions associated with acute pain (principal diagnoses, associated diagnoses and co-morbidities)
- Number and percentage of prescriptions associated with chronic pain (only principal diagnoses)

Contraindication for the use of NSAIDs or weak opioids

The patients' history will be evaluated for medical events referencing to contraindications for NSAIDs or weak opioids (such as myocardial infarction or stroke) for a timeperiod of 12 months prior to first prescription of Flupirtine. Only patients with a history of at least 12 months will be included in this analysis.

Analyses:

- Number and percentage of patients identified as contraindicated of NSAIDs/weak opioid treatment (such as myocardial infarction or stroke)

Long-term medications leading to contraindications for Flupirtin

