9.7.2.4 Comparison of the patient/prescriptions of the two observational periods

The comparison of the patients/prescriptions of the two observational periods (assessment period and reference period) based on IMS[®] Disease Analyzer data will consider the following parameters. The comparisons will be performed separately by physician panel and will be stratified by incident and prevalent users:

- Number and percentage of patients with any diagnosis of disease contraindicated for NSAIDs or weak opioids
- Number and percentage of prescriptions with diagnosis associated with acute pain
- Number and percentage of patients with single and repeated flupirtine prescriptions within the defined time period
- Number and percentage of prescriptions with LFT monitoring during flupirtine treatment
- Length of treatment episodes
- Number and percentage of patients with at least one treatment episode longer than 14 days (based on DDD)

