10.5 Does the plan describe methods for adjusting				

Section 10: Analysis plan	Yes	No	N/A	Page Number(s)
for confounding?				
10.6 Does the plan describe methods addressing effect modification?				

Comments:

--

Section 11: Data management and quality control	Yes	No	N/A	Page Number(s)
11.1 Is information provided on the management of missing data?				27
11.2 Does the protocol provide information on data storage? (e.g. software and IT environment, database maintenance and anti-fraud protection, archiving)				27
11.3 Are methods of quality assurance described?				31
11.4 Does the protocol describe possible quality issues related to the data source(s)?				
11.5 Is there a system in place for independent review of study results?				

Comments:

--

Section 12: Limitations	Yes	No	N/A	Page Number(s)
12.1 Does the protocol discuss:				
12.1.1 Selection biases?				32
12.1.2 Information biases?				32
(e.g. anticipated direction and magnitude of such biases, validation sub-study, use of validation and external data, analytical methods)				
12.2 Does the protocol discuss study feasibility?(e.g. sample size, anticipated exposure, duration of follow-up in a cohort study, patient recruitment)				13, 26
12.3 Does the protocol address other limitations?				32

Comments:

--

Section 13: Ethical issues	Yes	No	N/A	Page Number(s)
13.1 Have requirements of Ethics Committee/Institutional Review Board approval been described?				33

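### The 2012-versus-2014 comparison is crude for age and sex, so a change in patient mix can be read as a change in prescribing

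*Protocol*

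**What the plan says.** Section 9.1 fixes the design: "The study will be set up as a pre-post design to compare flupirtine prescribing patterns (before and after the revision of SmPC"). Section 9.7.1 says that parameters suited to comparing the two periods "with respect to the effect of risk minimisation measures" will be shown graphically.

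Section 9.7.2.4 lists six parameters for that comparison: the share of patients with a disease contraindicating NSAIDs or weak opioids, acute-pain diagnosis, single and repeated prescription, liver function testing, episode length, and any episode over 14 days. On control it says "The comparisons will be performed separately by physician panel and will be stratified by incident and prevalent users". Age and sex are not named there. They are extracted and described in 9.7.2.1: "Number and percentage of Flupirtine patients per age group, gender, insurance status(private or SHI insured").

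In Annex 2, "7.1 Does the protocol address known confounders?(e.g. collection of data on known confounders, methods of controlling for known confounders") is ticked N/A and the comment field of that section is empty. The item beginning "10.5 Does the plan describe methods for adjusting" (for confounding) is ticked No. The comment under checklist Section 3 reads "Only descriptive statistics will be done, no statistical tests". Section 9.9 does not mention a change in patient mix between the periods.

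**The concern.** The two periods contain different patients. Section 9.2 applies no exclusion criteria, so nothing holds the mix constant. Between the periods the indication was narrowed, and section 9.5 itself allows for a hypothetical 25% fall in prescriptions. A change in who receives the drug is therefore plausible on the protocol's own account.

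If a compared parameter varies with age or sex, a shift in mix moves its crude percentage even when patients of the same age and sex are treated exactly as before. A shift in the opposite direction can hide a real improvement. A reader of a contrast offered as bearing on the effect of the measures needs to tell two things apart: different patients were treated, or similar patients were treated differently. Separate age and sex tables reveal that the mix moved, but do not say how much of the change in another table follows from it.

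That is why N/A at 7.1 does not fit. Confounding applies to a difference in percentages whether or not a test is run on it.

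**Working it through.** **Inputs from the protocol.** Table 2 (section 9.5) gives patients with 12 months of history, reduced by 25%:
- PCP: 11,284 × 0.75 = 8,463 (stated 8,463).
- Orthopaedist: 1,821 × 0.75 = 1,365.75 (stated 1,365, truncated).

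The text rounds these to about 8,400 and 1,300 per period. They derive from July 2013 to June 2014; no 2012 count and no incident/prevalent split is given.

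**Assumed inputs.** The documents give no age shares and no age-specific rates. Everything below is illustration.

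**Mechanism.** With age-specific proportions unchanged, crude difference = (shift in age share) × (difference in proportion between the age groups concerned). Direct standardisation to the 2012 mix gives Σ w(2012) × p(2014), which equals the 2012 crude value here, so the standardised difference is 0.

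**Illustration A: a proportion with a steep age gradient.** Age shares 35/40/25% (<50, 50–69, 70+) and proportions 5/15/35%.
- 2012: 0.35×5 + 0.40×15 + 0.25×35 = 16.5%.
- 2014, after 5 points of patients move from <50 to 70+: 0.30×5 + 0.40×15 + 0.30×35 = 18.0%.
- Artefact: 1.5 points.
- Range: 3-point shift × 15-point gradient = 0.45 points; 10-point shift × 40-point gradient = 4.0 points.

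95% half-width for the period difference, 1.96 × √(2 × 0.165 × 0.835 / n), with equal n per period:

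| Group | n | Half-width (points) |
|---|---|---|
| PCP, whole panel | 8,463 | 1.12 |
| PCP, assumed 50/50 incident/prevalent | 4,231 | 1.58 |
| Orthopaedist, whole panel | 1,365 | 2.78 |
| Orthopaedist, assumed 50/50 | 682 | 3.94 |

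The 1.5-point artefact exceeds sampling error in the unsplit PCP panel, but not in a half-size PCP stratum, and not in the orthopaedist panel.

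**Illustration B: any episode over 14 days.** Proportion 40% in younger patients and 50% or 60% in those aged 70+; share aged 70+ falling from 30% to 25%, from 30% to 20%, or from 40% to 25%.
- Smallest: 5-point shift × 10-point gradient = 0.5 points.
- Middle: 0.30×60 + 0.70×40 = 46% against 0.20×60 + 0.80×40 = 44%, so 2.0 points.
- Largest: 0.40×60 + 0.60×40 = 48% against 0.25×60 + 0.75×40 = 45%, so 3.0 points.
- Half-width for 46% against 44%, 1.96 × √((0.46×0.54 + 0.44×0.56)/n): 1.50 points at n = 8,400, 2.13 at n = 4,200 (assumed 50/50 split), 3.82 at n = 1,300.
- Probability that the 95% interval excludes zero for artefacts of 2 to 3 points: about 0.74 to 0.97 at n = 8,400, and about 0.18 to 0.34 at n = 1,300.

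These half-widths assume simple random sampling.

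**The case against.** **The contraindication share is what the restriction is meant to change.** The narrowed indication concerns adults who cannot use NSAIDs or weak opioids. If prescribers move towards older patients with infarction or stroke, that is success, and age lies on the pathway. Standardising to the 2012 mix would remove the intended effect. This stands: for that parameter the crude share is the answer, and a standardised figure can only decompose it.

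**The study is descriptive.** No hypothesis is tested, no effect measure is defined, and the actual percentage in each period answers the aim of characterising prescribing. The phrase on the effect of the measures sits in a sentence about which results to plot. This justifies keeping the crude figures as the main result. It does not make confounding inapplicable, because that sentence is also the protocol's stated reason for comparing the periods.

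**Mix is partly handled.** Panel and user status are held by stratification, and the age and sex tables would expose a shift. This is true, and it narrows the gap to how much of a change the shift explains.

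**The checklist is weak evidence.** It is a supporting document. Item 10.5 truthfully describes the protocol, and item 10.4 answers No to stratified analyses although 9.7.1 stratifies all of them. On this point, however, the body text agrees with the ticks, and the checklist's own instructions ask for an explanation when N/A is chosen.

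**A separate SAP could add standardisation.** Section 9.8 mentions one. But the protocol does not leave the matter open: it marks confounding as not applicable.

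**Stronger readings.** A reader might infer that a mix change will be credited to the measures, or that it would exceed sampling error in the PCP panel. The documents support neither. They do not say that a crude change will be attributed to the measures, and the second claim depends on the unstated incident/prevalent split and 2012 count.

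**Conclusion.** The point holds in a limited form. The comparison is offered as bearing on the effect of the measures, it is crude for age and sex within panel and user stratum, and the checklist sets confounding aside without a reason. A change in age-sex mix can therefore be mistaken for a change in prescribing, or can mask one.

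This needs both a shift in mix and a parameter that varies with age or sex; the documents give figures for neither. Under the assumed inputs the artefact is about 0.5 to 4 points. In the PCP strata it may or may not exceed sampling error; in the orthopaedist panel it mostly would not. The crude figures are not wrong as descriptions of each period. What is missing is a simple way to separate who was treated from how similar patients were treated, using data that the study already extracts.

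**What to change.** In 9.7.2.4:
- Keep the crude figures as the main result.
- Beside them, give 2014 figures directly standardised to the 2012 age-by-sex distribution, within panel and incident/prevalent stratum, using broad groups merged from those in 9.7.2.1. Do this for repeat prescription, liver function testing, acute-pain diagnosis, mean episode length, and any episode over 14 days.
- For prescription- and episode-level parameters, classify each unit by the age and sex of its patient.
- For the NSAID/weak-opioid contraindication share, keep the crude figure as the answer; label any standardised figure as a decomposition only.
- Describe a crude change in a parameter of use that disappears after standardisation as a change in who was treated.

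In Annex 2, answer 7.1 as applicable and update 10.5. In 9.9, name case-mix change and secular trend as limitations; standardisation does not remove the latter.

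The cost is extra table columns and some sparse cells to merge; no new data and no tests are needed. Medians and ranges of episode length do not standardise in this simple way and stay crude. The standardised figure also removes any part of the effect that acts through patient selection, which is why the crude figure stays beside it.

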8.1.3 Covariates?				
8.2 Does the protocol describe the information available from the data source(s) on:				
8.2.1 Exposure?(e.g. date of dispensing, drug quantity, dose, number of days of supply prescription, daily dosage, prescriber)				17, 20, 22, 23
8.2.2 Endpoints?(e.g. date of occurrence, multiple event, severity measures related to event)				
8.2.3 Covariates?(e.g. age, sex, clinical and drug use history, co-morbidity, co-medications, life style, etc.)				20
8.3 Is a coding system described for:				
8.3.1 Diseases? (e.g. International Classification of Diseases (ICD)-10)				29
8.3.2 Endpoints?(e.g. Medical Dictionary for Regulatory Activities(MedDRA) for adverse events)				
8.3.3 Exposure? (e.g. WHO Drug Dictionary, Anatomical Therapeutic Chemical (ATC) Classification System)				29
8.4 Is the linkage method between data sources described? (e.g. based on a unique identifier or other)				

Comments:

--

Section 9: Study size and power	Yes	No	N/A	Page Number(s)
9.1 Is sample size and/or statistical power calculated?				

Comments:

--

Section 10: Analysis plan	Yes	No	N/A	Page Number(s)
10.1 Does the plan include measurement of excess risks?				
10.2 Is the choice of statistical techniques described?				14, 27
10.3 Are descriptive analyses included?				14, 27
10.4 Are stratified analyses included?				
10.5 Does the plan describe methods for adjusting				

Section 10: Analysis plan	Yes	No	N/A	Page Number(s)
for confounding?				
10.6 Does the plan describe methods addressing effect modification?				

Comments:

--

Section 11: Data management and quality control	Yes	No	N/A	Page Number(s)
11.1 Is information provided on the management of missing data?				27
11.2 Does the protocol provide information on data storage? (e.g. software and IT environment, database maintenance and anti-fraud protection, archiving)				27
11.3 Are methods of quality assurance described?				31
11.4 Does the protocol describe possible quality issues related to the data source(s)?				
11.5 Is there a system in place for independent review of study results?				

Comments:

--

Section 12: Limitations	Yes	No	N/A	Page Number(s)
12.1 Does the protocol discuss:				
12.1.1 Selection biases?				32
12.1.2 Information biases?				32
(e.g. anticipated direction and magnitude of such biases, validation sub-study, use of validation and external data, analytical methods)				
12.2 Does the protocol discuss study feasibility?(e.g. sample size, anticipated exposure, duration of follow-up in a cohort study, patient recruitment)				13, 26
12.3 Does the protocol address other limitations?				32

Comments:

--

Section 13: Ethical issues	Yes	No	N/A	Page Number(s)
13.1 Have requirements of Ethics Committee/Institutional Review Board approval been described?				33
13.2 Has any outcome of an ethical review procedure been addressed?				
13.3 Have data protection requirements been described?				13, 33

Comments:

--

Section 14: Amendments and deviations	Yes	No	N/A	Page Number(s)
14.1 Does the protocol include a section to document future amendments and deviations?				

Comments:

--

Section 15: Plans for communication of study results	Yes	No	N/A	Page Number(s)
15.1 Are plans described for communicating study results (e.g. to regulatory authorities)?				33, 34
15.2 Are plans described for disseminating study results externally, including publication?				33, 34

Comments:

--

Name of the main author of the protocol: [name]

Date: 24/09/2015

[name]

Signature: _____

